# STUDY INFORMATION

Title	Patient Characteristics, Adherence and Clinical Outcomes among People Living with HIV (PLWH) Initiating Cabotegravir + Rilpivirine LA regimen in the OPERA Cohort – Protocol Amendment	
Protocol version identifier	Amendment V3	
Date of last version of protocol	05 September 2024	
Active substance	Cabotegravir Rilpivirine	
Medicinal product	VOCABRIA® 30 mg film-coated tablets Edurant® 25 mg film-coated tablets Cabenuva	
Product reference  NDA 212887 VOCABRIA (cabotegravir) tablets  NDA 202022 EDURANT (rilpivirine) tablets  NDA 212888 CABENUVA (cabotegravir extended injectable suspension; rilpivirine extended injectable suspension), co-packaged, for intramususe		
Marketing authorisation holder(s)	ViiV Healthcare	
Research question and objectives	Using real-world clinical data from a large US cohort, this study will describe utilization, adherence and clinical outcomes among people with HIV initiating CAB+RPV LA regimen.	
Country(-ies) of study	United States	
Author	ViiV Healthcare PPD	

# MARKETING AUTHORISATION HOLDER(S)

Marketing authorisation holder(s)	ViiV Healthcare	
MAH contact person	PPD	

UNIQUE IDENTIFIER	216990	
TITLE	Patient Characteristics, Adherence and Clinical Outcomes among People Living with HIV (PLWH) Initiating Cabotegravir + Rilpivirine LA regimen in the OPERA Cohort – Protocol Amendment	
STUDY ACCOUNTABLE PERSON	Epidemiology and RWE	
CONTRIBUTING AUTHORS	PPD PPD , Epividian PPD , Epividian PPD PPD PPD , Epividian	
ASSET ID	GSK1265744, TMC278	
GSK ASSET	Cabotegravir + Rilpivirine LA (CABENUVA)	
EFFECTIVE DATE	23 April 2025	
INDICATION	HIV-1	
SAFETY OBJECTIVE	YES	

DATA COLLECTION TYPE	SECONDARY
TSS/PASS ASSESSMENT PERFORMED	Yes

Copyright 2024 ViiV Healthcare Company and the GlaxoSmithKline group of companies.

# **REVISION CHRONOLOGY**

Date	Version	Change(s) since last version
16 August 2021	Original	N/A
17 May 2024	Amendment 1	
 
Extending the study for additional 3 years
 
Study population:         
 
Including PWH 13 years and older
 
Excluding treatment naïve individuals
 
 
 
Primary objective:         
 
Factors associated with confirmed virologic failure is listed as a separate primary objective
 
 
 
Secondary objective:         
 
Sub-group analyses are listed as a secondary objective
 
 
 
Oral lead-in and oral bridging will not be assessed
 

05 September 2024	Amendment 2	
 
Secondary objective:         
 
Updated sub-group analyses by viral load stratification - VL <50 and ≥50 copies/mL at initiation
 
Study population:                 
 
Including PWH 18 years and older
 
Outcome definitions:

	CO	NFIDENTIAL
ViiV Healthcare		Protocol Final
		months following initiation of CAB+RPV LA regimen  Added confirmed virologic failure definition and included time points during 6 months, 6, 12, 24, 36, 48 and 60 months following initiation of CAB+RPV LA regimen  To regimen  Included additional time points 36, 48 and 60 months following initiation of CAB+RPV LA regimen  Included additional time points 36, 48 and 60 months following initiation of CAB+RPV LA regimen for maintaining virologic suppression and CVF definitions
23 April 2025	Amendment 3	Adding the following secondary objectives:  1. To compare baseline characteristics and treatment outcomes (persistence/discontinuation, adherence, maintaining virologic suppression, confirmed virologic failure) between oral ART and CAB+RPV LA use  2. To describe baseline characteristics and treatment outcomes (persistence/discontinuation, adherence, virologic effectiveness) among PWH on CAB+RPV LA in new subgroups of interest - Race/ethnicity (Non-Hispanic Black, Hispanic, Non-Hispanic White) and Sex/race (Non-Hispanic Black men, Hispanic men, Black women)  3. Among individuals with confirmed virologic failure

	CONTIDENTIAL
ViiV Healthcare	Protocol Final
	216990 – Amendment 3
	(CVF): to describe HIV
	resistance and proviral DNA
	testing at failure and history of
	resistance and proviral DNA
	testing
	4. Among individuals with
	confirmed virologic failure
	(CVF): to describe clinical
	characteristics and virologic
	outcomes on ART regimen after
	CVF
	• Study population:
	1. Including PWH prescribed with
	new oral guidelines-
	recommended ART regimens
	Too minima and that Too minima

#### **SUMMARY OF CHANGES**

#### Amendment 1:

"Patient characteristics, Adherence, and Clinical Outcomes among People Living with HIV (PLWH), Initiating Cabotegravir + Rilpivirine LA Regimen in OPERA cohort" (Study #216990) is a ViiV-sponsored two-year observational cohort study utilizing prospectively collected electronic health record (EHR) data obtained from the OPERA cohort that commenced in December 2020 (effective date: 16 August 2021).

The proposed plan is to extend the study for three years, from two years to five years, to assess the demographics, utilization patterns, persistence, adherence, and effectiveness of Cabotegravir (CAB) + Rilpivirine (RPV) LA in OPERA cohort over the first five years of availability of the regimen.

## Proposed changes to study population:

The proposed changes to the study population are listed below:

- 1. The initial study included people with HIV (PWH) 18 years and older and this study will include PWH who are 13 years of age or older so that we can describe the adolescent population.
- 2. The initial study included all individuals initiating CAB+RPV LA regimen and this study will only include the treatment experienced individuals as we did not observe any treatment naïve individuals initiating CAB+RPV LA in the initial study.

#### Proposed changes in study objectives:

The proposed changes to the study objectives are:

- 1. Primary objective:
  - a. Factors associated with confirmed virologic failure was not listed as a separate primary objective in the initial study but was assessed as part of virologic effectiveness analysis. It is called out as a separate primary objective in this study as we will enough numbers to conduct this analysis.
- 2. Secondary objective:
  - a. Sub-group analyses by viral load (<50 copies/mL, 50 <200 copies/mL, and ≥200 copies/mL), BMI (<30 and ≥30 kg/m²) and age (<18, 18-50, 50-64, ≥65 years) at initiation to assess characteristics, adherence, persistence, discontinuation and virologic effectiveness are explicitly called out as a secondary objective in this study. Some of the sub-groups listed were evaluated in the initial study but was not listed as a study objective.
- 3. Oral lead-in and oral bridging explored in the initial study will not be assessed in this study as these events cannot be reliably observed in the OPERA data.

#### Amendment 2:

## Proposed change in secondary objective:

The proposed changes to sub-group analyses include:

1. Updating viral load stratification for sub-group analyses to suppressed (VL <50 copies/mL) and viremic (≥50 copies/mL) at initiation.

## Proposed change to study population:

The proposed change to the study population is to include people with HIV (PWH) 18 years and older.

#### Proposed change in outcome definitions:

Among viremic  $(VL \ge 50 \text{ copies/mL})$  at initiation:

The proposed change is to update achieving virologic suppression definition, add virologic non-response and confirmed virologic failure definitions and add additional time points for individuals with VL≥ 50 copies/mL at initiation. This definition is consistent with HHS guidelines, our definitions for observational studies and the FDA's proposed assessments for ViiV's registrational study (CROWN) of CAB+RPV among individuals with viremia at regimen initiation.

- i. Achieving virologic suppression include only achieving suppression to <50 copies/mL, remove achieving suppression to <200 copies/mL and include additional time points 36, 48 and 60 months following initiation of CAB+RPV LA regimen
- ii. Non-response: VL ≥50 copies/mL after 6 and 12 months following initiation of CAB+RPV LA regimen and also no VL of <50 copies/mL during follow up will be described.
- iii. Confirmed virologic failure defined as:
  - a. Suppressed to <50 copies/mL followed by either 2 VLs ≥200 copies/mL or 1 VL ≥200 copies/mL and discontinuation within 4 months for every other month regimen; and discontinuation within 2 months for monthly regimen.
  - b. FDA's ask: suppressed to <50 copies/mL followed by either 2 VLs ≥400 copies/mL or 1 VL ≥400 copies/mL and discontinuation within 4 months for 2 monthly regimen; and discontinuation within 2 months for monthly regimen
  - c. Evaluate proportion of individuals with confirmed virologic failure (CVF) during the first 6 months, and at 6, 12, 24, 36, 48 and 60 months following initiation of CAB+RPV LA regimen

Among suppressed at initiation (VL<50 copies/mL):

ViiV Healthcare

Protocol Final 216990 – Amendment 3

The proposed update is to include additional time points 36, 48 and 60 months following initiation of CAB+RPV LA regimen for maintaining virologic suppression and CVF definitions among individuals with VL<50 copies/mL at initiation.

#### Amendment 3:

## Proposed changes in secondary objective:

The proposed changes include adding the following secondary objectives:

- 1. Comparing baseline characteristics and treatment outcomes (persistence/discontinuation, adherence, maintaining virologic suppression, confirmed virologic failure) between oral ART and CAB+RPV LA use
- 2. Additional sub-group analyses by Race/ethnicity (Non-Hispanic Black, Hispanic, Non-Hispanic White) and Sex/race (Non-Hispanic Black men, Hispanic men, Black women) to assess characteristics, adherence, persistence, discontinuation and virologic effectiveness.
- 3. Among individuals with confirmed virologic failure (CVF), describing HIV resistance and proviral testing at the time of CVF, as well as history of resistance and proviral DNA testing prior to CVF
- 4. Among individuals with confirmed virologic failure (CVF), describing clinical characteristics and virologic outcomes on ART regimens after CVF

## Proposed change to study population:

The proposed change to the study population is to include an additional group of individuals receiving a new oral ART regimen during the time period of interest.

# LIST OF ABBREVIATIONS

ADAP	AIDS Drug Assistance Program
AE	Adverse Event
AIDS	Acquired Immunodeficiency Syndrome
ART	Antiretroviral Therapy
BAA	Business Associate Agreements
BIC	Bictegravir
BMI	Body mass index
CAB	Cabotegravir
CD4	Cluster of Differentiation 4
CDC	Centers for Disease Control
CHORUSTM	Clinical Health Outcomes Reporting and Utilization Service
CMS	Centers for Medicare & Medicaid Services
ECAB	Epidemiology & Clinical Advisory Board
EHR	Electronic Health Record
FDA	Food and Drug Administration
FTC	Emtricitabine
HIPAA	Health Insurance Portability and Accountability Act
HITECH	Health Information Technology for Economic and Clinical
	Health
HIV	Human Immunodeficiency Virus
INSTI	Integrase Strand Transfer Inhibitor
IQR	Interquartile Range
IRB	Institutional Review Board
LA	Long Acting
mL	Milliliter
MIPS	Merit-based Incentive Payment System
MSM	Men who have Sex with Men
OPERA®	Observational Pharmaco-Epidemiology Research and Analysis
PHI	Protected Health Information
PWH	People with HIV
PWID	People Who Inject Drugs
RPV	Rilpivirine
QA	Quality Assurance
RNA	Ribonucleic Acid
TAF	Tenofovir
μL	Microliter
US	United States
VACS	Veterans Aging Cohort Study
VL	Viral load

# TRADEMARK INFORMATION

Trademarks of the ViiV Healthcare and GlaxoSmithKline group of companies	Trademarks not owned by ViiV Healthcare and the GlaxoSmithKline group of companies
CABENUVA TM	CHORUS™
VOCABRIATM	OPERA®

#### \*SYNOPSIS

\*Title Patient Characteristics, Adherence and Clinical Outcomes among People Living with HIV (PLWH) Initiating Cabotegravir + Rilpivirine LA regimen in the OPERA Cohort – Protocol Amendment

#### \*Rationale and background

The advancements in antiretroviral therapy (ART) over the past three decades have produced a marked reduction in both morbidity and mortality associated with HIV infection. To further improve HIV treatment options, recent clinical development has been focused on long-acting formulations. Cabotegravir + rilpivirine long-acting (CAB+RPV LA) injectable is the first complete long-acting antiretroviral regimen approved for treatment of HIV-1 in the US. It is indicated for people with HIV (PWH) who are virologically suppressed (HIV-1 RNA viral load [VL] <50 copies per mL) on a stable antiretroviral regimen, with no history of treatment failure and no known or suspected resistance to CAB or RPV. While clinical studies have established the efficacy, safety, and tolerability of CAB+RPV LA, this study will assess the utilization patterns, adherence, and effectiveness of this regimen in real-world clinical setting over the first five years of availability.

## \*Research question and Objective(s)

The overall objective of this study is to describe characteristics and assess clinical outcomes among people with HIV in the Observational Pharmaco-Epidemiology Research and Analysis (OPERA®) cohort who receive CAB+RPV LA regimen.

#### Primary Objectives:

- 1. To describe baseline demographics, clinical characteristics and patterns of use among PWH receiving CAB+RPV LA at Year 3, Year 4, and Year 5 of availability
- 2. To assess the persistence, adherence and discontinuation among PWH receiving CAB+RPV LA at Year 3, Year 4, and Year 5 of availability
- 3. To assess virologic effectiveness among PWH receiving CAB+RPV LA at Year 3, Year 4, and Year 5 of availability
- 4. To assess factors associated with confirmed virologic failure among PWH receiving CAB+RPV LA regimen at Year 3, Year 4, and Year 5 of availability

#### Secondary Objectives:

1. Sub-group analyses by viral load (VL <50, ≥ 50 copies/mL) at initiation, BMI (<30 and ≥30 kg/m²) at initiation and age (18-50, 50-64, ≥65 years) at initiation to assess characteristics, adherence, persistence, discontinuation and virologic effectiveness

- 2. To estimate the frequency of documented injection site reactions and hypersensitivity reactions among PWH receiving CAB+RPV LA injections at Year 3, Year 4, and Year 5 of availability
- 3. To compare baseline characteristics and treatment outcomes (persistence/discontinuation, adherence, maintaining virologic suppression, confirmed virologic failure) between oral ART and CAB+RPV LA use in PWH at Year 4 and Year 5 of availability
- 4. To describe baseline characteristics and treatment outcomes (persistence/discontinuation, adherence, virologic effectiveness) among PWH receiving CAB+RPV LA injections at Year 4 and Year 5, in subgroups of interest
- a) Race/ethnicity (Non-Hispanic Black, Hispanic, Non-Hispanic White)
- b) Sex/race (Non-Hispanic Black men, Hispanic men, Black women)
- 5. Among individuals with confirmed virologic failure (CVF): to describe HIV resistance and proviral testing at the time of CVF, as well as history of resistance and proviral DNA testing prior to CVF at Year 4 and Year 5 of availability
- 6. Among individuals with confirmed virologic failure (CVF): to describe the ART regimens after CVF in OPERA at Year 4 and Year 5 of availability
- a) To describe the baseline characteristics (demographic, clinical, treatment patterns) of ART regimen after CVF
- b) To describe virologic response (suppression, non-response, confirmed virologic failure) to ART regimen after CVF

#### \*Study Design

This is an observational study utilizing prospectively collected electronic health record (EHR) data obtained from the OPERA® cohort. The study population will include treatment experienced PWH who are 18 years or older, are active in care in OPERA, and received at least one CAB+RPV LA injection between 21JAN2021 and 31DEC2023, 21JAN2021 and 31DEC2024, and 21JAN2021 and 31DEC2025. PWH will be followed from the date of their first CAB+RPV injection until discontinuation of CAB+RPV regimen, death, loss to follow-up (12 months after last clinical contact), or study end (29FEB2024, 28FEB2025, and 28FEB2026).

#### \*Population

## For CAB+RPV LA:

#### Inclusion criteria:

- People with HIV
- $\geq$ 18 years old
- Treatment experienced
- Active in care in OPERA defined as having a clinical encounter in the 24 months prior to 31DEC2023, 31DEC2024, 31DEC2025

ViiV Healthcare Protocol Final 216990 – Amendment 3

• Received at least one CAB+RPV LA injection between 21JAN2021 and 31DEC2023, 31DEC2024, 31DEC2025

#### Exclusion criteria:

- Received CAB+RPV LA regimen as part of a clinical trial
- Treatment naïve

#### For Guidelines Recommended Oral ART:

#### Inclusion criteria:

- People with HIV
- ≥18 years old
- Treatment experienced
- Active in care in OPERA defined as having a clinical encounter in the 24 months prior to 31DEC2024, 31DEC2025
- Received a prescription for a new oral ART regimen (recommended by the DHHS guidelines as first-line therapy at the time of analysis)
- Virologically suppressed (VL <50 copies/mL) at start of new oral ART regimen

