#### Potential confounders to be evaluated:

 Baseline: age, gender, race, ethnicity, region, marital status, risk of HIV transmission, payer type, CD4 cell count, viral load, prior regimen, years since HIV diagnosis and ART initiation, weight, BMI, co-infections, comorbidities, concomitant medications

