#### 4. \*RATIONALE AND BACKGROUND

Antiretroviral therapy (ART) has transformed human immunodeficiency virus (HIV) infection from a fatal illness to a chronic disease.[1] The advancements in antiretroviral therapy (ART) over the past three decades have produced a marked reduction in both morbidity and mortality associated with HIV infection. Since then, the introduction of single-tablet regimens (STR) and once-daily dosing has been associated with increased adherence and improved clinical outcomes in HIV and other illnesses. To further improve HIV treatment options, recent clinical development has been focused on long-acting formulations; formulations that may be dosed once-weekly, once-monthly, and once-bi-monthly. Various routes of delivery for these long-acting formulations are currently being explored, including oral delivery, intravenous infusion, intra-muscular injection, subcutaneous injection, and implantable/removable device delivery.[2-6]

Cabenuva®, a 2-drug co-packaged product of Cabotegravir, a human immunodeficiency virus type-1 (HIV-1) integrase strand transfer inhibitor (INSTI), and Rilpivirine, an HIV-1 non-nucleoside reverse transcriptase inhibitor (NNRTI), is indicated as a complete regimen for the treatment of HIV-1 infection in adults to replace the current antiretroviral regimen in those who are virologically suppressed (HIV-1 RNA less than 50 copies per mL) on a stable antiretroviral regimen with no history of treatment failure and with no known or suspected resistance to either Cabotegravir or Rilpivirine.

The novel long-acting ART therapy delivered through intramuscular injection – CAB+RPV LA – has been shown to be non-inferior to daily oral therapy. Prior to starting the regimen, the healthcare provider (HCP) should carefully select people with HIV (PWH) who agree to the required injection schedule and counsel individuals about the importance of adherence to scheduled dosing visits to help maintain viral suppression and reduce the risk of viral rebound and potential development of resistance associated with missed doses.

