#### **Secondary Objectives:**

- 1. Sub-group analyses by viral load (VL <50, ≥50copies/mL) at initiation, BMI (<30 and ≥30 kg/m²) at initiation and age (18-50, 50-64, ≥65 years) at initiation to assess characteristics, adherence, persistence, discontinuation and virologic effectiveness
- 2. To estimate the frequency of documented injection site reactions and hypersensitivity reactions among PWH receiving CAB+RPV LA injections at Year 3, Year 4, and Year 5 of availability
- 3. To compare baseline characteristics and treatment outcomes (persistence/discontinuation, adherence, maintaining virologic suppression, confirmed virologic failure) between oral ART and CAB+RPV LA use in PWH at Year 4 and Year 5 of availability
- 4. To describe baseline characteristics and treatment outcomes (persistence/discontinuation, adherence, virologic effectiveness) among PWH receiving CAB+RPV LA injections at Year 4 and Year 5, in subgroups of interest
  - a. Race/ethnicity (Non-Hispanic Black, Hispanic, Non-Hispanic White)
  - b. Sex/race (Non-Hispanic Black men, Hispanic men, Black women)
- 5. Among individuals with confirmed virologic failure (CVF): to describe HIV resistance and proviral testing at the time of CVF, as well as history of resistance and proviral DNA testing prior to CVF at Year 4 and Year 5 of availability

ViiV Healthcare Protocol Final 216990 – Amendment 2

- 6. Among individuals with confirmed virologic failure (CVF): to describe the ART regimens after CVF in OPERA at Year 4 and Year 5 of availability
  - a. To describe the baseline characteristics (demographic, clinical, treatment patterns) of ART regimen after CVF
  - b. To describe virologic response (suppression, non-response, confirmed virologic failure) to ART regimen after CVF

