#### 6.3.3. Confounders and effect modifiers

#### 6.3.3.1. Confounders

The following baseline characteristics will be evaluated as potential confounders:

- Demographic characteristics at index
  - Age (years, as well as categorized as 18-50, 50-64, 65+)
  - Sex (male, female)
  - Race (African American/Black, Asian, White, other race, unknown)
  - Ethnicity (Hispanic, non-Hispanic)
  - Marital status (Single, married/domestic partner, widowed, separated/divorced, unknown)
  - Geographic region (Northeast, Midwest, South, West, US Territories)
  - Risk of HIV transmission (MSM, PWID, Heterosexual, Vertical, Other)
  - Payer type (Medicaid, Medicare, Commercial insurance, AIDS Drug Assistance Programs (ADAP)/Ryan White, Cash)
- Clinical characteristics at index
  - Years since HIV diagnosis
  - Years since ART initiation
  - AIDS diagnosis at baseline

- Years since first OPERA visit
- Veterans Aging Cohort Study (VACS) Mortality Index score
- Weight (kg)
- $\circ \quad BMI (<30 \text{ vs.} \ge 30 \text{ kg/m}^2)$
- Co-infections
  - Hepatitis B co-infection
  - Hepatitis C co-infection
  - Syphilis infection (ever)
- o Comorbidities
  - Autoimmune disease
  - Cardiovascular disease
  - Invasive cancer
  - Endocrine disorder
  - Mental health disorder
  - Liver disease
  - Bone disorder
  - Peripheral neuropathy
  - Renal disease
  - Hypertension
  - Substance abuse
  - Any of the above
- Concomitant Medications
  - Anticonvulsants
    - Carbamazepine
    - Oxcarbazepine
    - Phenobarbital
    - Phenytoin
  - Antimycobacterials
    - Rifampin
    - Rifapentine
    - Rifabutin
  - Glucocorticoids
    - Dexamethasone
  - Macrolide or ketolide antibiotics
    - Azithromycin
    - Clarithromycin
    - Erythromycin
  - Narcotic analgesic
    - Methadone
- ART regimens prior to CAB+RPV LA
  - Number of core agents experienced
  - o Number of ARV classes experienced
  - Duration of last ARV regimen
  - o Prior core agent class
- Baseline virologic characteristics
  - o HIV viral load
    - Test result available (yes/no)
    - Continuous (copies/mL and log10 copies/mL)

- Categorical
  - o <50 copies/mL
  - $\circ$   $\geq$ 50 to  $\leq$ 200 copies/mL
  - $\circ \geq 200 \text{ to } < 1,000 \text{ copies/mL}$
  - $\circ \ge 1,000 \text{ to} < 10,000 \text{ copies/mL}$
  - $\circ \ge 10,000 \text{ to } < 100,000 \text{ copies/mL}$
  - $0 \ge 100,000 \text{ copies/mL}$
  - Missing
- Baseline immunologic characteristics
  - o CD4 cell count

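### Prior virologic failure and CAB/RPV resistance, which the protocol names as conditions for CAB+RPV LA, are missing from both cohorts' criteria and from the confounder lists for the oral-ART comparison

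*Protocol*

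**What the plan says.** Section 5, secondary objective 3, sets up a comparison of persistence, adherence, maintained suppression and CVF "between oral ART and CAB+RPV LA use in PWH at Year 4 and Year 5 of availability".

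The Synopsis (Rationale and background) gives the conditions under which CAB+RPV LA is indicated: viral load (VL) <50 copies/mL on a stable regimen, "with no history of treatment failure and no known or suspected resistance to CAB or RPV". Section 4 repeats them: "with no history of treatment failure and with no known or suspected resistance to either Cabotegravir or Rilpivirine".

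The Synopsis (Population) requires oral comparators to be "Virologically suppressed (VL <50 copies/mL) at start of new oral ART regimen" and to start a regimen that the guidelines recommend as first-line. It excludes only clinical-trial receipt and treatment-naïve status. The CAB+RPV LA cohort needs at least one injection, with the same two exclusions. Section 6.2 merges the two sets of criteria and adds nothing on failure or resistance.

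The Synopsis list of potential confounders includes "CD4 cell count, viral load, prior regimen, years since HIV diagnosis and ART initiation". Section 6.3.3.1 opens with "The following baseline characteristics will be evaluated as potential confounders" and enumerates them in detail, down to individual anticonvulsants. Neither list names prior virologic failure or prior resistance. Section 6.3.2.7 tabulates earlier genotyping and resistance only in people who reach CVF.

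**The concern.** By the protocol's own account, earlier treatment failure and CAB or RPV resistance help decide who is a candidate for the injectable. Both also plausibly predict a new virologic failure. A variable that influences both cohort membership and outcome is a confounder, and here the protocol neither restricts on these two nor lists them.

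This is separate from whether the cohorts have the same baseline VL. A person can be suppressed at index and still have failed before or carry recorded resistance, so limiting both cohorts to VL <50 would not remove the problem.

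At stake is how objective 3 is read. A lower CVF proportion on CAB+RPV LA could partly reflect who was started on it, and the planned covariates could not separate that from the regimen.

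**Working it through.** **1. The two conditions across the protocol**

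| Place | Prior failure | Prior CAB/RPV resistance |
|---|---|---|
| Indication (Synopsis; section 4) | named | named |
| CAB+RPV LA criteria (Synopsis; 6.2) | absent | absent |
| Oral ART criteria (Synopsis; 6.2) | absent | absent |
| Confounder lists (Synopsis; 6.3.3.1) | absent | absent |
| 6.3.2.7 | absent | only among people with CVF |

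The nearest listed items are number of core agents and ARV classes experienced, duration of last regimen, prior core agent class, AIDS diagnosis and years since ART start. People also change regimens without failing, so these track failure and resistance only in part.

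**2. The protocol's own counts.** Section 6.5 gives 1,578 + 229 + 36 = 1,843 starters. Those with VL ≥50 at first injection are 229/1,843 = 12.4%, or 229/1,807 = 12.7% of those with a known VL. The indication was therefore not followed on VL in at least 12.4%. The protocol gives no corresponding figure for failure or resistance history, no CVF rate and no oral cohort size.

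**3. Size, by assumption.** Let pC and pO be the shares of CAB+RPV LA and oral starters with prior failure or resistance, and R the CVF risk ratio for that history. With no true difference between regimens, the crude CVF ratio (CAB+RPV LA/oral) is

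[1 + pC(R − 1)] / [1 + pO(R − 1)].

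All values of pC, pO and R below are assumptions.

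| pC | pO | R | Calculation | Ratio |
|---|---|---|---|---|
| 2% | 10% | 2 | 1.02/1.10 | 0.93 |
| 5% | 10% | 3 | 1.10/1.20 | 0.92 |
| 5% | 20% | 3 | 1.10/1.40 | 0.79 |
| 5% | 30% | 4 | 1.15/1.90 | 0.61 |
| 10% | 10% | any | equal | 1.00 |
| 10% | 5% | 3 | 1.20/1.10 | 1.09 |

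With an assumed base CVF risk of 2%, the 5% versus 20% row gives 2% × 1.10 = 2.20% on CAB+RPV LA and 2% × 1.40 = 2.80% on oral ART. That is a gap of 0.60 percentage points with no true effect.

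These ratios are crude. They credit the listed proxies with removing nothing, and the residual bias after adjusting for them cannot be estimated from the protocol.

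**The case against.** A reader might infer that the comparison is biased towards the injectable and stays so after matching on VL and adjusting for everything listed. The documents do not support that, for four reasons:

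- **Direction.** It depends on prescribers following the label, which the cohort criteria do not require, and 12.4% of starters were outside it on VL. Prevalence of prior failure or resistance is given for neither cohort. If more CAB+RPV LA starters had such a history, the bias would run the other way.
- **Analysis.** The protocol describes no matching and no adjusted oral-versus-injectable model. Section 6.7.1.1 gives unadjusted Poisson rates and a logistic model for factors associated with CVF. The comparison model may be in the SAP.
- **First-line restriction.** Limiting the oral cohort to first-line regimens may keep out some people whose history calls for something else. That could narrow the gap by an unknown amount.
- **Purpose.** Section 6.9.1 calls these descriptive analyses, and the lists are of potential confounders to be evaluated.

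All four stand as limits on direction and size. They do not remove the gap. Restricting the regimen does not restrict the person's history. Low label adherence on VL does not show that failure and resistance history are balanced. Section 6.7.1.1 does allow other variables, but only for stratification. The confounder list is stated in this protocol, in both Synopsis and body, and it omits two selection factors that the same protocol names. An objective that compares outcomes invites attribution, even in a descriptive study.

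**Conclusion.** The point holds as an omission from the stated confounder lists. Secondary objective 3, run as written, is open to confounding by indication through prior virologic failure and prior CAB/RPV resistance, and the listed items address this only in part.

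The bias probably favours the injectable if prescribing follows the label, but neither sign nor size is established. Ratios of 0.93 to 0.61 illustrate what an excess of such history among oral starters could do before any adjustment. Equal prevalence gives 1.00, and an excess among CAB+RPV LA starters gives more than 1. All of these rest on assumed prevalences and risk ratios.

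The point concerns one secondary objective and leaves the primary objectives, which describe CAB+RPV LA alone, untouched. The correction is cheap and would also show whether the imbalance exists, so it should be made before the comparison is reported.

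**What to change.** Add two baseline variables, for both cohorts, to the Synopsis list and section 6.3.3.1:

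- **Prior virologic failure before index**, derived from the OPERA history and consistent with the CVF rule in section 6.3.2.6: two consecutive VLs ≥200 copies/mL, or one VL ≥200 copies/mL plus discontinuation. A single raised value alone should not count. Section 6.3.2.4 defines discontinuation only by days since last injection, so the derivation must state how it is determined for earlier oral regimens.
- **Recorded resistance to CAB or RPV before index**, coded yes / no / never tested or unknown.

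Tabulate both by cohort, and include both in whatever adjusted or weighted oral-versus-CAB+RPV LA comparison is made. As a sensitivity analysis, report the objective 3 virologic outcomes in people of both cohorts with VL <50 at index and neither history recorded. Section 6.7.1.2, which currently plans none, would need to change. Label this subset as having no recorded history, not as eligible for either option, because it includes untested people.

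Cost: no new data collection, but genotype history must be extracted for both full cohorts and not only for people with CVF. History before the first OPERA visit is incomplete, so some confounding will remain, and the restricted subset is smaller.
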